The Control Condition: The same physical training and BCTs support will be arranged for the control group.

Instruments and Measures:

Participants will be assessed on a variety of outcomes (described below) at 1 week and at 1 and 3 months (T1 – T3) after the programme, which will be compared with the baseline assessment (T0). The participants will be asked to wear an ActiGraph Wgt3x accelerometer on their non-dominant wrist for 7 days before the commencement of any intervention, as well as during each outcome assessment time point.

Socio-demographic data: The following data will be collected: 1) data on age, gender, marital status, exercise habits, living conditions, and level of education, 2) the participants' health-related information, including their morbidities, cognitive status, medications, and number of hospital and out-patient clinic visits in the past 12 months.

Feasibility:

To understand the feasibility of this intervention, the frequency with which the participants in the experimental group use the tracker over the time of the study (i.e., 112 days), the recruitment rate, the attrition rate, the participants' adherence to the exercise regimen, and reports of adverse effects will be monitored.

Primary outcome measurement: Activity levels

The participants' physical activities and sedentary time will be objectively measured using a ActiGraph wGT3X accelerometer.

Secondary outcome measurements

Fitbit Data (only participants in the experimental group): The total steps per week, total walking distance per week, and time spent in different heart rate zones (50-69%, 70-84%, and >85% of the maximum heart rate) of an individual will be collected.

Physical Endurance: This will be evaluated using different physical tests:

1. The participants' lower-limb muscle and upper-limb strength will be assessed using a 30-second chair stand test and a handheld Jamar Hydraulic Hand Dynamometer, respectively.
2. Mobility will be assessed through the Timed-up-and-Go (TUG) test and by their gait speed (2-m walk). These two tests assess the overall performance of the lower limbs and walking speed, which can reflect the effect of exercise in enhancing the participants' overall physical endurance.

Exercise Self-efficacy: The participants' self-confidence in their ability to exercise in a variety of circumstances (e.g., even when they were feeling tired) will be assessed using the Chinese Self-Efficacy for Exercise scale (CSEE).

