Frailty status: This will be assessed based on Fried's frailty five phenotypes as mentioned in the sample inclusion criteria. **Physical activity level** is one criterion of frailty that will be assessed using the 10-item PASE-C to measure self-reported occupational, household, and leisure activities for the last week.

Self-reported sedentary behavioral and physical activity: This will be assessed using the Global Physical Activity Questionnaire-Chinese version (C-GPAQ), which comprises 16 questions designed to estimate an individual's self-perceived level of physical activity in three domains (occupational, transport-related and discretionary or leisure time).

Motivation to engage in physical activity: This will be assessed by the 19-item Chinese version of the Behavioral Regulation in Exercise Questionnaire-2 (C-BREQ-2). The C-BREQ-2 is a 19-item questionnaire assessing five dimensions: amotivation, external regulation, introjected regulation, identified regulation, and intrinsic regulation. Each item is rated on a 5-point scale ranging from 0 = "not true for me" to 4 = "very true for me", with higher scores indicative of higher motivation.

Procedures: Ethical and access approval will be obtained from the Ethics Review Committee of The University and study venues, respectively. Potential participants will be referred to the research team by the community centres. An RA will screen all potential participants for their eligibility to participate in this study. Written informed consent will then be obtained from all of the participants, to whom all aspects of the study will be explained and questions answered. They will then be interviewed to obtain their demographic data, and baseline assessment. After that, the participating community centres will be randomized to either the control or experimental group. Participants from each centre will be placed into their centre's corresponding group to avoid 'contamination' effects across participants. At 1 week, 1 month, and 3 months post-intervention, an independent assessor who is blinded to the group allocations will assess the participants' outcomes, which will be compared with the baseline assessment. Another RA will collect all "Fitbit activity-related data" from the participants in the experimental group every week. All of the participants in the experimental group will be invited to attend the focus group interviews, which will be conducted by JS after the first post-test T1 and T3.

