Official Title: Enhancing physical activity levels of community-dwelling older people with frailty through an exercise intervention with or without a wearable activity tracker (WAT)-based intervention: a feasibility and pilot study

Date of the document: 22/03/2018

Approved by the Human Subjects Ethics Sub-committee of The Hong Kong Polytechnic University on 13/04/2018

Statistical Analysis:

SPSS version 23.0 will be used to analyse the data. Descriptive statistics will be generated for the demographic data and feasibility tests. The baseline characteristics of the participants in the two groups from the six community centres will be compared using unpaired t test for the continuous variables, a chi-square test for the categorical variables, and the Mann-Whitney U test for the ordinal variables. Normality assumptions for the variables will be examined by a K-S test. The group attendance and drop-out rate of the participants in the study groups will be reported. An intention-to-treat analysis will be adopted. An independent sample Student's t-test or Mann-Whitney U test will be used to examine differences between the control and experimental groups in the outcome variables. For categorical and dichotomous outcome variables, an χ^2 test will be used to test differences between the groups. If significant differences between the groups at baseline have been identified, these data will be treated as covariates and adjusted for as needed. A p-value of < 0.05 will be considered statistically significant. ANOVA will be used to measure the effectiveness of the intervention. If the data were non-normal, Friedman's test will be used instead. Post-hoc within-group comparisons will be done using paired t-tests or Wilcoxon's signed rank test, and Bonferroni adjustments will be made.

Content analysis will be used to analyse the interview data. All audio-taped interviews will be transcribed into Cantonese by the RA and the transcriptions will be checked for accuracy by two members of the research team before the analysis.

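### Baseline accelerometer activity becomes a covariate only if a baseline test is significant, so the primary comparison is usually not adjusted for it

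*SAP*

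**What the plan says.** The SAP compares the arms at baseline with participant-level tests: "The baseline characteristics of the participants in the two groups from the six community centres will be compared using unpaired t test" for continuous variables, with other tests for categorical and ordinal ones. It then makes adjustment depend on the result: "If significant differences between the groups at baseline have been identified, these data will be treated as covariates and adjusted for as needed". The threshold is p < 0.05. No variable is named as a covariate in advance.

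The SAP does not say whether T0 values of the outcomes count among the baseline characteristics to be tested. If they do not, T0 activity can never become a covariate.

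For the main analysis the SAP says only that "ANOVA will be used to measure the effectiveness of the intervention", and "If the data were non-normal, Friedman's test will be used instead". Separately, it lists t-tests or Mann-Whitney tests between the arms.

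In the Protocol, under Instruments and Measures, the accelerometer is worn "for 7 days before the commencement of any intervention, as well as during each outcome assessment time point". The same section says of the T1-T3 outcomes: "which will be compared with the baseline assessment (T0". Under Procedures, the sequence is consent, then baseline assessment, and then: "After that, the participating community centres will be randomized to either the control or experimental group". The Sample size paragraph adds that researchers do not know the allocation until baseline measurement is finished.

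**The concern.** T0 activity is measured before allocation, so it is a valid covariate, and any T0 difference between arms arises by chance. What makes a covariate useful is how well it predicts follow-up. A test of the difference between arms does not measure that. The rule therefore selects on the wrong quantity, and even a significant result leaves the final decision to adjust open.

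Two readings of the main analysis are possible. If follow-up values alone are compared, a T0 imbalance carries over into the estimate. If T0 is a time level in a repeated-measures ANOVA, the comparison between arms is one of change from T0. That over-corrects the imbalance whenever the slope of follow-up on T0 is below 1. The SAP does not say which reading applies, and neither adjusts for T0.

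The Protocol justifies its sample size by the need to estimate an effect size, and a larger main study is to follow. The main harm is a less reliable planning estimate.

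**Working it through.** **Inputs from the documents.** 60 participants in six centres, with centres randomised 1:1 (Protocol, Sample size). This is taken as 3 v 3 centres of 10, or 30 v 30 participants. The significance level is 0.05 (SAP), taken as two-sided. The plan gives no figure for how often adjustment would occur, and its sample size has no formula to reproduce.

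**Assumed, because the documents give neither.** Correlation r between T0 and follow-up of 0.5 or 0.7, and an ICC of 0, 0.05 or 0.10, the same at T0 and follow-up. Data are normal with equal SDs and there is no treatment effect. Results marked as simulated use 200,000 trials per setting.

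**Step 1: how often T0 is left out, if it is tested.** The design effect is DE = 1 + (10 - 1) x ICC. The chance of a non-significant test is about 2Φ(1.96/√DE) - 1.

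| ICC | DE | Formula | Simulated |
|---|---|---|---|
| 0 | 1.00 | 95.0% | 95.0% |
| 0.05 | 1.45 | 89.6% | 89.6% |
| 0.10 | 1.90 | 84.5% | 84.1% |

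**Step 2: largest imbalance left unadjusted at ICC 0.** t(0.975, 58) x √(2/30) = 2.0017 x 0.2582 = 0.52 SD.

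**Step 3: error given the imbalance, ICC 0.** For a T0 imbalance of d SD, the follow-up-only comparison is off by r x d, the change comparison by -(1 - r) x d, and the adjusted comparison by 0.

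- Over all unflagged trials the mean absolute imbalance is 0.186 SD (simulated). Follow-up only: 0.5 x 0.186 = 0.093 and 0.7 x 0.186 = 0.130. Change: -0.5 x 0.186 = -0.093 and -0.3 x 0.186 = -0.056. The simulated values are 0.093 / 0.131 and -0.093 / -0.054.
- In the 28% of trials with an unflagged imbalance above 0.25 SD, the simulated errors are 0.175 / 0.246 (follow-up only) and -0.176 / -0.105 (change).
- For scale, the standard error of a follow-up-only comparison is √(2/30) = 0.26 SD.

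**Step 4: variance.** Against never adjusting, at ICC 0, adjustment leaves 1 - r² = 75% / 51% of the follow-up-only variance and (1 + r)/2 = 75% / 85% of the change variance. The fair comparator is the SAP's own rule, which already adjusts flagged trials. The simulated reductions from always adjusting, for r = 0.5 / 0.7, are:

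| Setting | Rule on change from T0 | Rule on follow-up only |
|---|---|---|
| ICC 0 | 19% / 10% | 18% / 41% |
| ICC 0.05, T0 predicts centre differences | 15% / 8% | 14% / 34% |
| ICC 0.10, T0 predicts centre differences | 12% / 6% | 12% / 29% |
| ICC 0.05, T0 does not predict them | 20% / 13% | 4% / 9% |
| ICC 0.10, T0 does not predict them | 18% / 12% | about 0% |

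At ICC 0 the simulated standard errors are 0.250 / 0.241 (rule, follow-up only), 0.250 / 0.196 (rule, change) and 0.225 / 0.186 (always adjusted). As a check, 1 - (0.186/0.196)² = 10%.

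**Step 5: where adjustment does not remove the error.** If T0 varies between centres but does not predict their follow-up, the adjusted estimate is itself off in trials with an unflagged imbalance above 0.25 SD. The error is 0.05 / 0.08 SD at ICC 0.05 and 0.08 / 0.11 SD at ICC 0.10. The follow-up-only errors there are 0.12 / 0.17 and 0.09 / 0.12 SD.

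**The case against.** The 95% figure only restates the 5% significance level and is not itself a harm. That is right: the harm lies in steps 3 and 4. Those two steps also describe one phenomenon from two sides, because chance imbalance is already part of the unadjusted standard error. They must not be added together. The average unflagged error in a follow-up-only comparison, 0.09 / 0.13 SD, is a third to a half of that standard error.

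The repeated-measures design, the stated comparison with T0 and the pairing of ANOVA with Friedman's test make T0 as a time level the likelier reading. On that reading the variance gain with clustering is 6-20%, or about 3-11% of the standard error (1 - √0.94 to 1 - √0.80). The larger figures need the follow-up-only reading, which the separate t-test sentence leaves open.

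The gain depends on unknown correlations. At r = 0.3 it is about 5% against follow-up only at ICC 0, and between -1% and 4% with clustering, although 18% or more against change.

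Finally, this is a small pilot with mainly descriptive feasibility aims. That limits the stakes but does not remove them, because the sample size rests on estimating an effect size. None of these points defends the significance trigger itself.

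**Conclusion.** The point holds. The rule chooses covariates by a test that carries no information about their value, and T0 activity is not otherwise pre-specified. The rule causes no bias over all randomisations. Its cost is a predictable error given the imbalance that occurs and, in most settings, lost precision.

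Under r of 0.5 to 0.7 and an ICC of 0.05 to 0.10, always adjusting reduces variance by about 6-20% against the rule applied to change and by 0-34% against the rule applied to follow-up only. At ICC 0 the figures are 10-19% and 18-41%. In the least favourable setting examined at these correlations, adjustment neither gains nor materially loses. The reading of the rule is certain. The size of the gain rests on the assumed correlations and ICC.

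**What to change.** - Delete the significance-triggered covariate rule.
- Pre-specify that each continuous outcome compared between arms and measured at T0 is analysed with its own T0 value as a participant-level covariate, whatever the baseline tests show. For the primary outcome this is T0 ActiGraph activity. The tracker data are outside this rule because they exist in one arm only: "Fitbit Data (only participants in the experimental group".
- State that T0 is a covariate and not a time level. A longitudinal model with T0 as an outcome and a common baseline mean across arms would serve equally well, provided one approach is fixed in advance.
- For outcomes that would move to a non-normal test, state how T0 is still used, for example the same adjusted comparison after a pre-stated log or rank transformation of T0 and follow-up.
- State how participants with missing or invalid T0 wear data are kept, for example by imputing the overall T0 mean without regard to arm.

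The cost is SAP wording and one individual-level degree of freedom. T0 is already collected. The change does not correct for ignored clustering by centre, which is a separate point.

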Although the ultimate goal of using WATs should be increased MVPA, such data was not reported in previous studies on older people. Moreover, the suggested additional measures for facilitating the adoption of WATs by older people have not previously been tested. It is worth testing the efficacy of a combined intervention of exercise training plus WAT intervention in which BCTs have been incorporated. Little is presently known about the efficacy of using a WAT intervention among older people with frailty. The main hypothesis is that the WAT intervention plus exercise training programme will increase physical activity levels compared to an exercise programme alone. If we are successful in proving the hypothesis, we will propose studying the long-term effects (i.e., increased daily MVPA and the adoption of a physically active lifestyle) of this intervention in the main study with a larger sample size with a longer follow-up period.

B. Research plan and methodology (Appendix 1: Consort Research Flowchart)

Aim: A single-blinded, repeated-measures, two-arm pilot cluster RCT is proposed to examine the feasibility and preliminary effects of an exercise programme with or without a WAT intervention for promoting physical activity levels among community-dwelling older people with frailty. To explore the acceptability of the WAT intervention, a focus group with all participants in the experimental group (4-6 people per group) will be interviewed by JS (the Co-I).

Subjects and Settings: A district community health centre will be viewed as one unit/cluster. Eligibility criteria for district community health centres are those that are funded by the Hong Kong (HK) government and under the supervision of the Social and Welfare Department of HK, and thus that meet a specific set of standard regulations and criteria on environment and practices. Six community centres, which provide similar types of community care and social support services for community-dwelling older people, will be invited by a convenience method to work as collaborators in this study. The target population of this study are community-dwelling older people with frailty who will be recruited through the community centres.

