Sample size: Teare et al., 2014 recommended that a pilot study is required a total number of participants between 60 and 100 when estimating the effect size for a continuous outcome. Thus, sixty participants will be recruited from six community centres. We estimate that about 25-50% of the members of these centres will be eligible to participate (Schultz-Larsen et al., 2007; Liu, 2017). We will target moderate to large centres with the total number of centre members around 800. Given that we can screen 200 older people (50 in each centre) per 4 to 6 weeks, and based on our previous study in similar centres (Liu et al., 2017), we believe that we will need about 3 to 4 months to recruit 60 participants (with 30 subjects recruited per 4 to 6 weeks in two-three centres) for this study. Given the difficulty of obtaining details of the backgrounds of all potential participants in these community settings, a properly random sample cannot be implemented. Thus, convenience sampling will be used to recruit participants among the collaborative community centres. Using computer-generated random numbers, a biostatistician not affiliated with this study will randomize the centres in a 1:1 ratio into either: the control or the experimental groups. Participants from each centre will be placed in their centre's corresponding group to avoid 'contamination' effects across participants. To avoid selection biases, the allocation to the study groups will be concealed from the researchers until sample recruitment and baseline measurements have been completed. Appendices 1 and 2 show the CONSORT research flow chart and the timeline of this study.

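### On the non-normal branch the SAP's effectiveness test is Friedman's test, which cannot compare the two arms; the between-arm test it also lists is not tied to a visit or scale

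*SAP*

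**What the plan says.** The hypothesis is stated at the end of Protocol section A: "The main hypothesis is that the WAT intervention plus exercise training programme will increase physical activity levels compared to an exercise programme alone". This is a contrast between arms. The control is active; under The Control Condition the Protocol says "The same physical training and BCTs support will be arranged for the control group". Outcomes are measured at baseline (T0) and then "at 1 week and at 1 and 3 months" after the programme (T1 to T3), and no visit is named as primary.

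The SAP's Statistical Analysis section has three relevant elements:

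- **Effectiveness test:** "ANOVA will be used to measure the effectiveness of the intervention. If the data were non-normal, Friedman's test will be used instead". The factors of the ANOVA are not given.
- **Between-arm test:** an independent t-test or "Mann-Whitney U test will be used to examine differences between the control and experimental groups in the outcome variables". No visit is given, nor a choice between raw values and change from baseline.
- **Follow-up tests:** "Post-hoc within-group comparisons will be done using paired t-tests or Wilcoxon's signed rank test, and Bonferroni adjustments will be made".

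Nothing says which of these decides the question. The Protocol's Sample size section rests the 60 participants on a recommendation that "a pilot study is required a total number of participants between 60 and 100 when estimating the effect size for a continuous outcome". It also states that a biostatistician "will randomize the centres in a 1:1 ratio into either: the control or the experimental groups".

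**The concern.** Friedman's test is a one-sample repeated-measures test. Whether all 60 participants are pooled or each arm is run separately, it asks whether the outcome differs between visits. It has no group term and no group-by-visit term, so it cannot address the stated hypothesis, and it yields no between-arm effect size for planning a main study.

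The active control makes this more than a technicality. If the shared exercise programme works, both arms improve, and a test of change over time will tend to be significant whether or not the tracker adds anything. Running the test within each arm and reading significance in the WAT arm but not in the control arm as a tracker effect is not a valid between-arm test either.

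Protocol section A says that success on the hypothesis would lead to a larger, longer study. No statistical progression rule is set, so the harm is a pilot result that is misread.

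**Working it through.** **1. The plan's own figure.** The documents give no power, SD or expected difference, so N = 60 cannot be reproduced by a formula. It is the lower end of the cited 60–100 range. The structural point does not depend on it.

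**2. Where arm enters Friedman's statistic.** With n people, k visits and R_j the sum over people of the within-person rank of visit j,

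Q = [12 / (n·k·(k+1))] Σ R_j² − 3n(k+1), referred to chi-square on k − 1 df.

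For n = 60 and k = 4, 12/(60·4·5) = 0.01 and 3·60·5 = 900. So Q = 0.01·Σ R_j² − 900 on 3 df, and arm does not appear. As a check, shuffling the arm labels 1,000 times in one simulated trial left the pooled Friedman p-value at 0.0473 every time, while the Mann-Whitney p-value ranged from 0.0003 to 1.0.

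**3. How often it would mislead.**

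- From the documents: 60 participants, six centres randomised 1:1, four visits, significance at p < 0.05.
- Assumed: 30 per arm, ten per centre, SD 1 on a transformed scale, an equal shift at T1 to T3, no attrition, no centre effect, and exchangeable within-person correlation of 0.4, 0.6 or 0.8.
- 10,000 trials per cell; tests two-sided where that applies.

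Percentage of trials with the stated result, at correlation 0.4 / 0.6 / 0.8:

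| True situation | Result | % of trials |
|---|---|---|
| Both arms +0.2 SD | Pooled Friedman p < 0.05 | 21 / 30 / 57 |
| Both arms +0.3 SD | Pooled Friedman p < 0.05 | 45 / 63 / 91 |
| Both arms +0.5 SD | Pooled Friedman p < 0.05 | 89 / 98 / 100 |
| Both arms +0.3 SD | Friedman in WAT arm p < 0.05 | 23 / 33 / 60 |
| Both arms +0.3 SD | Significant in WAT arm, not in control | 18 / 22 / 24 |
| WAT +0.6, control 0 | Significant in WAT arm, not in control | 71 / 86 / 95 |
| WAT +0.9, control +0.3 | Significant in WAT arm, not in control | 77 / 67 / 39 |
| Both arms +0.3 SD | Mann-Whitney on T3 change | 5 / 4 / 5 |
| WAT +0.6, control 0 | Mann-Whitney on T3 change | 52 / 70 / 94 |
| WAT +0.9, control +0.3 | Mann-Whitney on T3 change | 53 / 69 / 94 |

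In the two situations where the WAT arm exceeds control by 0.6 SD, the between-arm test gives nearly the same power. The within-arm pattern moves with the shared gain instead. With log-normal data (2,000 trials, correlation 0.6), a gain of 0.5 SD in the WAT arm and an equal loss in control made pooled Friedman significant in only 3.1% of trials, against 96% for Mann-Whitney at T3.

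**4. The open choices in the Mann-Whitney test.** Three visits × two scales = 6 versions. With no tracker effect, the smallest of the six p-values falls below 0.05 in 21.5% / 21.3% / 20.1% of trials. For six independent tests it would be 1 − 0.95⁶ = 26.5%. If the scale is fixed at change, the best of three visits gives about 12%.

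**5. A test that respects centre randomisation.** A t-test on six centre means has 6 − 2 = 4 df and critical t 2.78, against 2.00 on 58 df. Take a 0.6 SD WAT effect, correlation 0.6 and no centre ICC:

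- T3 change: variance 2(1 − 0.6) = 0.8; SE = √[(0.8/10)·(2/3)] = 0.231; 0.6/0.231 = 2.60; power 51%.
- Baseline-adjusted T3: variance 1 − 0.6² = 0.64; SE = √[(0.64/10)·(2/3)] = 0.207; 0.6/0.207 = 2.90; power 59%.

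At an assumed centre ICC in change of 0.05, the simulated powers are 37% and 41%. False-positive rates there are 5% for the centre-mean tests and 10% for Mann-Whitney.

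**The case against.** The best defence is that the SAP already has a between-arm test for non-normal outcomes. Read in order, it gives between-group tests, then ANOVA or Friedman over visits, then within-group follow-up. On that reading Friedman is the within-arm omnibus test and the only fault is the word effectiveness. Further, no text says that a within-arm result will be taken as a tracker effect, or that the smallest of six p-values will be reported. The Protocol's Instruments and Measures and Procedures sections compare later visits with baseline, which points to change scores. The branch is entered only if the K-S check fails. This is a feasibility pilot.

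Much of this stands:

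- A between-arm test does exist, and the rates in step 3 apply only if the ANOVA/Friedman line is followed as labelled.
- The 21% is a worst case.
- How often the branch is entered is unknown. For log-normal data at n = 60, an uncorrected K-S test rejects in about 2%, 17%, 68% and 90% of samples at assumed log-scale SDs of 0.3, 0.5, 0.8 and 1.0.
- The Sample size section does not say that the effect size is between arms; that is an inference, though the natural one for a two-arm trial.
- The ANOVA's unstated factors are an omission, not evidence that group was left out.

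What fails is the claim that the text already resolves the matter. The SAP attaches effectiveness to ANOVA/Friedman and does not call Friedman descriptive. The comparison with baseline is not tied to the Mann-Whitney test and does not choose a visit.

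**Conclusion.** The concern holds. As written, the non-normal branch assigns the effectiveness question to a test that cannot answer it. That conclusion follows from the form of the statistic and needs no assumptions.

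The sizes do rest on assumed inputs. A shared gain of 0.2 to 0.5 SD with no tracker effect makes pooled Friedman significant in 30% to 98% of trials at correlation 0.6. If Mann-Whitney is used instead, its false-positive rate depends on how the open choices are made: about 5% for one pre-named version with no centre effect, about 12% for the best of three visits on change, and about 21% for the best of all six.

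This should be fixed before analysis. It does not threaten the feasibility aims, and wording alone cures it.

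**What to change.** Amend the SAP as follows:

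1. Remove Friedman's test as the effectiveness analysis. Keep it and the within-arm paired tests as descriptive.
2. Name one between-arm analysis for both branches: the baseline-adjusted outcome at one stated primary visit, reported as a difference with a 95% confidence interval, with skewed continuous outcomes transformed.
3. Make it respect randomisation by centre. One option is a mixed model with group, visit, group-by-visit and baseline value, random participant and centre effects, and small-sample degrees of freedom. The other is a t-test on the six baseline-adjusted centre means.
4. State the ANOVA's factors, or replace the ANOVA with this model.
5. If Mann-Whitney is kept, define it as change from baseline at the stated visit and label it a sensitivity analysis that ignores clustering.
6. Transformation does not help ordinal outcomes such as frailty category, so state their between-arm analysis separately.

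No extra data are needed. The costs are results on a transformed scale, wider intervals, and power below the 70% of Mann-Whitney in the case worked in step 5. That 70% is not a like-for-like benchmark, because Mann-Whitney does not hold its 5% level once centres differ. For a pilot of this size, the estimate and its interval will be more useful than the p-value.
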